
Study Endpoints
	
Primary Safety/Tolerability Endpoint:
 
Safety/Tolerability will be assessed by the non-inferiority of incidence of serious adverse events (SAEs), unanticipated SAEs(USAEs), device-related SAEs (DSAEs) and Unanticipated Device Related SAEs (UDAEs) that are associated with the TENS therapy throughout the stimulation and the follow-up period versus historical control (compared with other TENS systems).
 
Safety variables will be tabulated and presented for all subjects including enrolled, but discontinued, subjects. Number of subjects undergoing active stimulation and any reasons for discontinuation of study treatment will be tabulated.
 
Safety/Tolerability will be assessed through 6 months of therapy.
 
Primary Effectiveness Endpoint:
 
The primary efficacy endpoint is the percent reduction in appetite suppression as measured by percent change in appetite scores at the end of 3 months of the Therapy period compared to Baseline between Treatment and Control.
 
A co-primary endpoint will be total body weight loss (%TBWL), measured as End Weight – Initial Weight divided by Initial Weight, multiplied by 100, at the end of 3 months of the Therapy period compared to Baseline between Treatment and Control.
 
Secondary Effectiveness Endpoints:
 
Number of subjects reporting >5% total body weight loss at the end of 3 months of the Therapy compared to Baseline between Treatment and Control
 
Blood pressure, blood lipids, and HbA1c at the end of 3 months of the Therapy compared to Baseline between Treatment and Control groups.
 
% changes in BMI at the end of Therapy compared to Baseline between Treatment and Control groups
 
Ancillary Endpoints:
 
Cross validation between smartphone app hunger scales and paper VAS diaries collected at the same times.
 
Changes between the following values:
 
Ease of use/prevalence of use errors associated with the patch unit and dietary application during initial training.
 
Subject preference scores at the end of Therapy compared to Baseline between Treatment and Control groups.

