The Kaplan Meier estimator will be utilized to compare decrease in %Total Body Weight Loss (&TBWL) and appetite scores between treatment and control subjects. Maximum likelihood statistics will be utilized to correct for censoring. Z statistics will be calculated to ensure lack of skewness or curtosis and square root arc sine transformations will be undertaken on the data if required prior to analysis.

Figure 2: Study Outline

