8.1.2 Analysis Populations

The intent to treat (ITT) analysis population is defined as all subjects who were enrolled.

The modified intent to treat (mITT) analysis population is defined as all subjects who initiated therapy (i.e., initiated their first Treatment Period Visit) and had data through week 12. All safety and effectiveness analyses will be completed on the mITT analysis population.

The per protocol (PP) analysis population is defined as all subjects who met all inclusion/exclusion criteria, completed all visits in the study without any major protocol deviations. All effectiveness analyses will be completed on the PP analysis population.

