8.1.3 Safety Analyses

The primary safety endpoint is defined as the proportion of subjects free of TENS-related serious adverse events and adverse device effects through the therapy phase, safety success rate. The success rates will be compared between groups using chi-square test or Fisher's exact test, as appropriate.

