8.2 Justification of Sample Size

As per the protocol, the calculation sample size for the study is based on conservative imputation of results from other studies on weight loss including the use of TENS for weight loss. The degree of coaching/dietary support throughout the present study is moderate intensity lifestyle/weight coaching. The sample size modeling assumes an average of 3.5% TBWL in Control Subjects using diet and exercise alone. The estimated weight loss in Treatment Subjects is modeled from preliminary data on T6/T7 dermatomal TENS when used for

weight loss: 6% TBWL. The variance of the responses in the study (i.e. Standard Deviation) was modeled at +/- 5% TBWL. This value was taken from previous dermatomal TENS weight loss study results. The model assumes a 30% drop out rate across groups and an 80% powered endpoint using an adaptive p spending model wherein interim posterior probability assessments are allowed after enrolling proscribe cohorts of not less than 67% of subjects. The alpha penalty will be minimized per interim by assessing the relationship between stimulation (i.e. dose) and weight loss using Normalized Linear Dynamic Modeling (NLDM) to determine overall sample size projected (i.e. futility) rather than assessing the primary hypothesis per se. Monotonicity will not be assumed in this analysis. This modeling provides an estimate of 80 subjects per group, for a total study size of 160 subjects. However, the protocol allows for enrollment of additional subjects should the interim model project under powering of the primary endpoint.

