Safety analyses will be conducted an Intent to Treat (ITT) basis (i.e. all subjects who were enrolled). Primary and Secondary effectiveness analyses will be performed on a modified intent-to-treat basis (MITT; i.e. all subjects who initiated therapy, defined as subjects who initiated their first Treatment Period Visit) as will all per subject effectiveness analyses (e.g. responder analyses). Primary and Secondary endpoints (e.g. weight loss, appetite) will also be conducted on a completer, or per protocol basis (defined as those subjects that completed all visits in the study).

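### Primary safety is a crude 24-week event-free proportion with no rule for incomplete follow-up, on contradictory safety sets; if event-free dropouts count as free, Treatment safety is overstated

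*Combined protocol and SAP*

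**What the plan says.** Section 8.1.3 takes as the primary safety endpoint the "proportion of subjects free of TENS-related serious adverse events and adverse device effects through the therapy phase". The analysis is binary: "The success rates will be compared between groups using chi-square test" or Fisher's test. The therapy phase lasts about 24 weeks (section 5), and the Protocol Summary promises evidence of safety over six months of use.

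The plan names two safety sets. Section 8.1.2, repeated in the SAP text inside the Protocol Summary, says: "All safety and effectiveness analyses will be completed on the mITT analysis population". It limits mITT to subjects who started therapy and have data through week 12. Section 8.4 says: "Safety analyses will be conducted an Intent to Treat (ITT) basis (i.e. all subjects who were enrolled". The Protocol Summary and section 6.1.1 side with the wider set for tabulation: "Safety variables will be tabulated and presented for all subjects including enrolled, but discontinued, subjects".

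On incomplete follow-up, section 8.2 states: "The model assumes a 30% drop out rate across groups". Section 8.3 limits imputation to the co-primary efficacy endpoints and says that partial data from dropouts are kept. The only method for censored data is in section 5 and is meant for efficacy: "The Kaplan Meier estimator will be utilized to compare decrease in %Total Body Weight Loss", together with appetite scores.

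**The concern.** A proportion free of events through week 24 can be read directly only if everyone is observed to week 24. A Treatment subject who leaves in week 2 without an event says nothing about weeks 3 to 24. If that subject stays in the denominator as a success, the reported rate mixes subjects who used the device for six months with subjects who barely used it. It is then higher than the event-free probability under six months of use.

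Control subjects receive no device, so they are close to 100% free of TENS-related events by construction. The distortion therefore falls on the Treatment arm and narrows the difference between groups. It would also favour the device in the comparison with historical controls that section 6.1.1 describes, for which no margin or reference rate is given.

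If the mITT set is used instead, anyone without data through week 12 is absent from the primary safety result. That can include people who left because of the device.

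**Working it through.** **The plan's own figures.** The plan states no safety rate, margin or safety power, so there is no safety figure to reproduce. The 30% dropout comes from the sample size for the 3-month weight endpoint. With means of 6% and 3.5%, SD 5, 80% power and two-sided 5% (alpha is not stated; assumed from the 95% two-sided intervals), n = 2 × (1.96 + 0.8416)² × 5² / 2.5² = 62.8, so 63 per arm. Then 63 × 1.3 = 82, close to the stated 80, whereas 63 / 0.7 = 90. The 30% was therefore probably applied to a 12-week endpoint. The plan gives it no time horizon.

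**Assumptions.** True 24-week risk P in Treatment: the plan gives no figure, and section 10.1.2 says only that events should be infrequent, so 2% to 30% is used. The event hazard is constant, h = -ln(1 - P)/24 per week. Dropout is d = 0.30 and unrelated to risk. Event-free dropouts are scored as free, and events before dropout are counted.

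**All-enrolled set.** Crude event rate = 0.7P + 0.3 × mean of [1 - exp(-hu)] over dropout time u. For u uniform on 0 to 24 weeks, the mean is 1 - P/(-ln(1 - P)). At P = 0.20 this is 1 - 0.2/0.22314 = 0.1037. The crude rate is 0.14 + 0.3 × 0.1037 = 0.171, so the event-free share reads 82.9% against a true 80.0%.

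| True risk | True event-free | Crude, dropout even over 24 weeks | Overstatement (points) | Dropout even over 12 weeks | All dropout on day 0 (0.3P) |
|---|---|---|---|---|---|
| 2% | 98.0% | 98.3% | 0.3 | 0.4 | 0.6 |
| 5% | 95.0% | 95.7% | 0.7 | 1.1 | 1.5 |
| 10% | 90.0% | 91.5% | 1.5 | 2.2 | 3.0 |
| 20% | 80.0% | 82.9% | 2.9 | 4.4 | 6.0 |
| 30% | 70.0% | 74.2% | 4.2 | 6.5 | 9.0 |

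**Early events.** Suppose 80% of events fall evenly in weeks 0 to 4, the rest fall evenly afterwards, and dropout is even over 24 weeks. The average share of events already seen at dropout is (4/24) × 0.4 + (20/24) × 0.9 = 0.817. The overstatement is 0.3 × P × 0.183 = 0.055P: about 0.6, 1.1 and 1.7 points at 10, 20 and 30%.

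**Dropout related to risk.** If dropouts carry twice the hazard and leave evenly over 24 weeks, the overstatement is 2.7, 5.0 and 6.7 points at base risks of 10, 20 and 30%.

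**mITT set.** With even dropout, 15% leave before week 12 and are removed, and 15% leave later. At P = 0.20, the mean of 1 - exp(-hu) over weeks 12 to 24 is 0.154. The crude rate is (0.15 × 0.154 + 0.7 × 0.20)/0.85 = 0.192, an overstatement of 0.8 points. At 10% and 30% it is 0.4 and 1.2 points.

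**The other counting rule.** If event-free dropouts are removed from the denominator while dropouts with events stay, then at P = 0.20 with even dropout the rate is 0.171/(0.70 + 0.031) = 23.4%. Risk is now overstated, so the direction reverses.

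**The case against.** The strongest objection is that the plan never says an event-free dropout is scored as free through week 24. Section 8.3 could be read as leaving such subjects unclassified, and scoring them as successes is itself a form of imputation. This stands as a limit. Keeping all enrolled subjects, including those who discontinued, with no imputation makes success the natural reading. It remains an inference, and the opposite rule reverses the bias.

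Second, section 8.1.2 would exclude the week-2 leaver, so the mechanism would reach only later dropouts. That also stands. It makes the shift in the rate smaller but removes early leavers from safety.

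Third, device-related events largely cannot begin after use stops, and a dropout with a recorded device effect already counts as a failure. As observed incidence among subjects as they used the device, the crude proportion is valid. It does not answer the question of safety under six months of use, which the protocol says the trial will show.

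A reader might infer that the plan overstates safety by many points at a 30% dropout over 24 weeks. The documents do not support that. They give the 30% no time horizon and state no event rate. The larger figures need risks near 30% with very early or risk-related dropout. Section 9.12.1 says that tingling or burning is typical. If these sensations were recorded as device effects, events would be common but early, which shrinks the bias.

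**Conclusion.** The concern holds in a limited form. The primary safety analysis ignores incomplete follow-up, and the plan contradicts itself on who is analysed. On the all-enrolled set, provided event-free dropouts count as free, the Treatment event-free rate is too high as an estimate of 24-week safety. The amount is about 0.3 to 4.2 points for assumed true risks of 2% to 30%, under a constant hazard and 30% dropout that is even over 24 weeks and unrelated to risk. It is less if events cluster early, and more if dropout is early or related to risk. On the mITT set it is about 0.4 to 1.2 points at risks of 10% to 30%, and the exclusion of early leavers becomes the larger problem.

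The direction depends on the unstated counting rule and the size on an unstated event rate. The documents therefore do not show that the reported rate will be materially biased. They do show that the method fits the six-month question poorly and that a better one is cheap.

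**What to change.** Reconcile section 8.1.2 and the matching SAP text in the Protocol Summary with section 8.4. Primary safety should use one set that keeps early leavers: all enrolled subjects, as section 8.4 says and as the Protocol Summary and section 6.1.1 already tabulate.

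In section 8.1.3, add a Kaplan-Meier or cumulative-incidence estimate of the 24-week event-free probability in Treatment with a 95% confidence interval. Time runs from Visit 1 to the first qualifying event and is censored at the last adverse-event assessment. Add a sensitivity analysis that counts as events those withdrawals for device intolerance not already recorded as an adverse device effect. Keep the crude proportion as the descriptive, as-used incidence, and state how event-free dropouts are classified.

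The cost is SAP wording and a short program. Adverse events are assessed at every visit (Appendix 6), so last-assessment dates should be available; event onset dates are also needed. The main downside is that Kaplan-Meier assumes censoring is unrelated to risk, which the sensitivity analysis addresses only in part. It also does not adjust for the pauses in stimulation that the protocol allows for skin irritation.

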To further understand the time points and weekly diary entries on appetite suppression, all time points and weekly entries will be analyzed in a repeated measures analysis of variance (RMANOVA) for each of the four appetite suppression endpoints separately. The RMANOVA will not use percentage changes but will use the actual appetite suppression scores with a factor for group treatment, time (week and time point), as well as the interaction factor between time and treatment.

The occurrence rate for subjects experiencing >5% TBWL at the end of 3 months will be compared between groups using chi-square test or Fisher's exact test, as appropriate.

Blood pressure, blood lipids, and HbA1c at the end of 3 months of the Therapy compared to Baseline between groups using t-tests or Wilcoxon rank sum tests, as appropriate.

The percent change from baseline in BMI at the end of 3 months of the Therapy compared to Baseline between groups using t-tests or Wilcoxon rank sum tests, as appropriate.

Exploratory Efficacy Summaries

Summary statistics will be provided by visit and by group for the other time points (besides the 3 month time point) for percent change from baseline in appetite suppression scores, %TBWL, occurrence rate for >5% TBWL, blood pressure, blood lipids, and HBA1c. In addition, summary statistics will be provided by visit and by group for ease of use, prevalence of use errors associated with patch unit and dietary application, and preference scores.

8.2 Justification of Sample Size

As per the protocol, the calculation sample size for the study is based on conservative imputation of results from other studies on weight loss including the use of TENS for weight loss. The degree of coaching/dietary support throughout the present study is moderate intensity lifestyle/weight coaching. The sample size modeling assumes an average of 3.5% TBWL in Control Subjects using diet and exercise alone. The estimated weight loss in Treatment Subjects is modeled from preliminary data on T6/T7 dermatomal TENS when used for

weight loss: 6% TBWL. The variance of the responses in the study (i.e. Standard Deviation) was modeled at +/- 5% TBWL. This value was taken from previous dermatomal TENS weight loss study results. The model assumes a 30% drop out rate across groups and an 80% powered endpoint using an adaptive p spending model wherein interim posterior probability assessments are allowed after enrolling proscribe cohorts of not less than 67% of subjects. The alpha penalty will be minimized per interim by assessing the relationship between stimulation (i.e. dose) and weight loss using Normalized Linear Dynamic Modeling (NLDM) to determine overall sample size projected (i.e. futility) rather than assessing the primary hypothesis per se. Monotonicity will not be assumed in this analysis. This modeling provides an estimate of 80 subjects per group, for a total study size of 160 subjects. However, the protocol allows for enrollment of additional subjects should the interim model project under powering of the primary endpoint.

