Study Design	
Randomized, adaptive parallel arm study. Subjects will be initially screened during a screening period (+/- 7 days). During this screening period, subjects will sign an Informed Consent Form (ICF), have their weight/height and blood pressure measured as part of a physical exam, take a pregnancy test (females of child bearing potential), get blood drawn for analysis (blood lipids, HbA1c), and complete the PHQ-9 and pre-study survey. Subjects will be asked to complete their first batch of diaries to set a baseline hunger value.
 
At the end of the screening period, eligible subjects will be enrolled/randomized in the study and be randomized to either a treatment or control group. After enrolling, both control and treatment subjects will be instructed to follow a healthy diet and reduce calories as desired for the duration of the study and will receive training on the use of the electronic scale and completion of paper diaries. For the treatment group, subjects will be instructed on use of the Elira wearable patch system. Photographs will be taken at the enrollment visit. Following this, subjects will enter the Therapy Period for ~24-weeks.
 
At the 12 week visit, subjects will be assessed for weight loss, blood pressure, blood lipids, HbA1c, patient preference questionnaire and their participation will continue through months 4-6 for the Safety phase of the Therapy Period. The Therapy Period will be considered complete (pending laboratory results, adverse events or serious adverse events). Patient (treatment) photographs will also be taken at the 12 week visit.

Protocol #: CD-005; Version #: 4.0

Original Date: May 8, 2018 Revision Date: May 3, 2019

-Confidential-

	
The study utilizes an adaptive approach where cohorts of enrolled/randomized subjects (in groups of ~25 per arm) are assessed for dose response and progression to achievement of primary and secondary endpoints. Frequent interim endpoint assessment utilizing Markov-chain Monte Carlo (MCMC) methods coupled with Longitudinal analyses will be utilized to determine sample sizes for future cohorts (assessed primarily via Normal dynamic linear modeling [NDLM]). Long term safety of the device will be shown through 6 months of usage.

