Subject Population / Sample Size	
The primary endpoints are powered at a final enrollment of 75 subjects per group, for a total of 150 subjects, but interim analyses based on Bayesian posterior probability distributions with multiple imputation will be utilized to assess interim significance.
 
In the event the interim analysis is not significant, up to 300 subjects may need to be enrolled in order to achieve final separation between groups for statistical significance. Thus, Elira may need to screen up to 500 subjects to account for exclusions prior to enrollment.

Study Duration and Sites	
Minimum study duration for each patient will be 25 weeks. As it is expected that recruitment of 150 subjects will take up to 24 weeks, the overall study duration is anticipated to be a minimum of 37 weeks, assuming all cohorts are enrolled. The study will be conducted at up to 10 centers.

Inclusion Criteria	
Subject is between 18 – 65 years of age inclusive.
 
Subject has a BMI of 25-35 kg/ m² inclusive.
 
Subject has signed the informed consent form and is able to comply with study protocol and adhere to study visit schedule.
 
Subject is able to wear and use a wearable, patch TENS system.
 
Subject is able to use a touch screen hand held smart phone.
 
Subject is fluent in English and can complete patient questionnaires.
 
Subject is male or non-pregnant, non-lactating female, who agrees to use effective contraceptive methods throughout the length of the trial based on PI approval.
 
Females of childbearing potential (FOCBP) must have a negative urine pregnancy test at screening or enrollment visit, prior to placement of ELIRA device.

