8. STATISTICAL CONSIDERATIONS AND ANALYSIS PLAN

8.1.1 General Methods

Categorical variables will be summarized by number and percent. Continuous variables will be summarized by total number (N), mean, standard deviation (SD), median, minimum and maximum. Ninety-five percent, 2-sided confidence intervals will be reported, as appropriate.

As this was a randomized trial, the groups are expected to be balanced on demographic and baseline characteristics. No formal testing for this is planned.

Planned analyses and summaries for the primary safety endpoint, co-primary efficacy endpoints, secondary efficacy endpoints and exploratory efficacy endpoints are detailed below.

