8.3 Handling of Missing Data

Every effort will be made to collect all data at each time point in the study. The PI and the Clinical Data Monitor will minimize the amount of missing data by appropriate management of the prospective clinical trial, proper screening of subjects, and training of clinicians. If a subject misses a dietary entry in to either the paper or electronic diary, a look back entry for that value is allowed provide for the week preceding the event. Outside this window, data will be considered missing. All partial data available for subjects who drop out during the course of the study will be included.

Missing data will only be imputed for the co-primary endpoints. The LOCF method will be utilized at the 3 month time point for the two co-primary endpoints of percent change from baseline in appetite suppression scores and %TBWL. The ANCOVA analysis with LOCF on the mITT population for the co-primary endpoints were planned for the main analyses for the study to determine study success. Note, however, by definition, the mITT population may not need LOCF as only those with a week 12 visit will be included in the mITT population. A patient, however, may have had a week 12 visit but have missing data on some or all co-primary endpoints, in which case LOCF methods will be used.

To assess the potential effect of missing data on the co-primary effectiveness endpoints, a tipping point analysis will be computed for each co-primary endpoint on the mITT population. If none of the 5 co-primary endpoints are missing at week 12, the tipping point analysis will be a moot point and will not be conducted. A tipping point analysis involves imputing each missing data point, one-at-a-time until the study conclusion is tipped in the other direction (i.e., from statistically significant to non-statistically significant or vice versa, from non-statistically significant to statistically significant).8.4 Subject Population for Safety and Effectiveness Analysis

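### The plan gives two powered sample sizes, 75 and 80 per group, and omits the alpha, sidedness and dropout timing needed to check either one

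*Combined protocol and SAP*

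**What the plan says.** The Protocol Summary (Subject Population / Sample Size) states: "The primary endpoints are powered at a final enrollment of 75 subjects per group, for a total of 150 subjects". Section 8.2, and the same text in the Statistical Analysis part of the Protocol Summary, states: "This modeling provides an estimate of 80 subjects per group, for a total study size of 160 subjects". Both are current text.

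Section 8.2 assumes mean weight loss of 3.5% in control and 6% in treatment, with an SD of 5. It adds: "The model assumes a 30% drop out rate across groups and an 80% powered endpoint". It attributes the result to an adaptive design with interim posterior-probability looks, and it shows no formula or operating characteristics.

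No alpha or sidedness is given for the sample size. The nearest statement, in Section 8.1.1, is a reporting convention: "Ninety-five percent, 2-sided confidence intervals will be reported, as appropriate".

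The endpoint is measured at 3 months, but the Study Design summary says: "Following this, subjects will enter the Therapy Period for ~24-weeks". The 30% is not tied to either time.

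The plan is also inconsistent on whether dropouts leave the main analysis. Section 8.1.2 defines mITT as "all subjects who initiated therapy (i.e., initiated their first Treatment Period Visit) and had data through week 12", and Section 8.3 says "only those with a week 12 visit will be included in the mITT population". Section 8.4 defines it by starting therapy alone, with no week-12 requirement, and Section 8.3 also says that partial data from dropouts will be used.

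**The concern.** Two different sizes are each presented as the powered one, and a reader cannot tell which governs enrolment or what power it delivers. The omitted inputs are not minor. Depending on how they are filled in, the same stated means, SD and dropout put both sizes above 80% power or both below it.

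The Protocol Summary also says that the primary endpoints, in the plural, are powered. Assumptions are given only for weight loss. No effect size or SD appears for any of the four appetite scores, although any one of them can make the study a success.

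**Working it through.** **Inputs from Section 8.2.** Difference δ = 6 − 3.5 = 2.5 points; SD σ = 5; standardised effect 2.5/5 = 0.5; power 80%; dropout 30%; equal groups.

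**Assumptions (not in the plan).** Fixed-sample two-group t-test, no alpha spent at interims and no multiplicity adjustment. Alpha, sidedness and the loss by week 12 are varied below.

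**Trying to reproduce 80 or 75.** Normal approximation, two-sided 0.05:

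m = 2(1.960 + 0.842)² / 0.5² = 62.8, so 63 evaluable per group. The t-test needs 63.8, so 64.

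Inflating for 30% loss with N = m/(1 − 0.30):
- Two-sided 0.05: 63/0.7 = 90; t-test 64/0.7 = 91.4, so 92.
- One-sided 0.05: 50/0.7 = 71.4, so 72; t-test 51/0.7 = 72.9, so 73.

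Neither 80 nor 75 comes out exactly, though the one-sided 73 is close to 75. Multiplying by 1.3 instead of dividing by 0.7 gives 63 × 1.3 = 81.9, which is near 80. That may be where the figure came from, but the plan shows no formula, so this is only a guess.

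**Power at each stated size.** With m evaluable per group, power is the probability that a noncentral t with 2m − 2 degrees of freedom and noncentrality 2.5 / (5√(2/m)) exceeds the critical value.

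| Assumption | 80 per group | 75 per group |
|---|---|---|
| Two-sided 0.05, all 30% lost by week 12 | 56 evaluable: 74.6% | 52.5 evaluable: 71.8% |
| Two-sided 0.05, 30% is a 24-week figure at a constant rate | 66.9 evaluable: 81.9% | 62.7 evaluable: 79.4% |
| Two-sided 0.05, 15% lost by week 12 | 68 evaluable: 82.5% | 63.75 evaluable: 80.0% |
| One-sided 0.05, all 30% lost by week 12 | 56 evaluable: 83.8% | 52.5 evaluable: 81.6% |

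In the second row, retention at week 12 is √0.7 = 0.837, or 16.3% lost; 80% power then needs 64/0.837 = 76.5, so 77 per group.

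**Loss each size can absorb at two-sided 0.05.** For 80 per group: 1 − 64/80 = 20%. For 75 per group: 1 − 63.8/75 = about 15%. The plan states neither rate.

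**If dropouts stay in through LOCF (the Section 8.4 reading).** At 80 per group, with the SD held at 5 and two-sided 0.05, power depends on how much of the effect the 30% carry:
- full effect: difference 2.5, power 88%;
- half: 0.7 × 2.5 + 0.3 × 1.25 = 2.125, power 76%;
- none: 0.7 × 2.5 = 1.75, power 60%.

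**At the enrolment cap.** 150 per group × 0.7 = 105 evaluable, two-sided 0.05: power 95%.

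**The case against.** The strongest reply is that no arithmetic error has been shown. Section 8.2 credits the 80 to an adaptive model, and a fixed-sample t-test does not compute that design's power. Enrolment can also grow: "In the event the interim analysis is not significant, up to 300 subjects may need to be enrolled". At that cap the fixed-sample figure is 95%. This stands to the extent that the 72% and 75% are conditional on assumed inputs. They are not the power of the design. But the plan shows no operating characteristics or interim alpha cost, and at a given size, spending alpha at interims lowers the fixed-sample figures. The option to enlarge the trial does not settle which starting size is right.

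A second reply is that 75 has a natural source. Cohorts are about 25 per arm, so 75 is three cohorts, and a one-sided requirement of 72 to 73 would round up to it. That is plausible, but the plan does not say so, and 80 would still conflict with it.

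Third, the unstated alpha could be smaller than assumed here. If 0.05 were split over the five primary tests (two-sided 0.01, an assumption), power at 56 evaluable would be about 51%. If it were not split, the chance of meeting the any-one-of-five success rule is at least the %TBWL power. Both points are fair, and both are reasons to state the alpha.

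ANCOVA does not clearly rescue the figures. The plan claims no variance gain, and the named covariate, %TBWL at baseline, is zero for everyone by definition.

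**Conclusion.** The concern holds. The conflict between 75 and 80 per group needs no assumptions. With n/(1 − d) inflation for the stated 30% loss, neither figure is reproduced exactly under two-sided or one-sided 0.05.

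The shortfall itself is conditional. It is 5 to 8 points below 80% if the test is two-sided at 0.05, all 30% are lost by week 12 and those subjects leave the analysis. It disappears at both sizes with one-sided 0.05, or if loss by week 12 is no more than about 15%. The plan should correct this, but the trial has not been shown to be underpowered.

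**What to change.** 1. Use one sample size in the Protocol Summary, Section 8.2 and the SAP text.
2. State the alpha, the sidedness, and the time point to which the 30% dropout applies. Reconcile the mITT definitions in Sections 8.1.2 and 8.3 with the one in Section 8.4.
3. Recompute and restate the power of the chosen size from those inputs. If they are two-sided 0.05 with 30% lost by week 12, that is about 75% at 80 per group or 72% at 75. If the 30% refers to week 24, give the week-12 loss assumed; under two-sided 0.05, 80% power holds only up to 20% loss at 80 per group, or about 15% at 75. If one-sided 0.05 was used, say so (84% and 82%).
4. Limit the power claim to %TBWL.

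This is a text change with no added patients, provided the restated power is accepted; the stated power may become less favourable. If the sponsor wanted to keep 80% under two-sided 0.05 with 30% lost by week 12, the size would be 92 per group, 184 in total, which is 24 more than 160.
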